eGFR	Estimated Glomerular Filtration Rate
FAS	Full Analysis Set
hsCRP	High-sensitivity CRP
IMP	Investigational Medicinal Product
IRB	Independent Review Board
LOCF	Last Observation Carried Forward
MDA	Malondialdehyde
MPO	Myeloperoxidase
MedDRA	Medical Dictionary for Regulatory Activities
n.a.	Not applicable
NTproBNP	N-terminal Propeptid BNP

STATISTICAL ANALYSIS PLAN

Protocol No: MEIN/14/FEB-PWV/001 (FORWARD)

Version Number: 2.0

Date of Issue: 2018-03-16

Page 7 of 22

Abbreviation	Description
Ox-LDL	Oxidized Low-Density Lipoprotein cholesterol
PON1	Paraoxonase 1
PON2	Paraoxonase 2
PP	Per-Protocol
PWA	Pulse Wave Analysis
PWV	Pulse Wave Velocity
PT	Preferred Term
QC	Quality Control
SAE	Serious Adverse Event
SAF	Safety Analysis Set
SAP	Statistical Analysis Plan
SAS	Statistical Analysis Software package
SD	Standard Deviation
SOC	System Organ Class
SOP	Standard Operating Procedure
sICAM	Soluble Intercellular Cellular Adhesion Molecule
sUA	Serum Urate Concentration
sVCAM	Soluble Vascular Cell Adhesion Molecule-1
TEAE	Treatment Emergent Adverse Event
TLFs	Tables, Listings, Figures
TMF	Trial Master File
TNF- α	Tumour Necrosis Factor Alpha
TS	Trial Statistician
TSH	Thyroid Stimulating Hormone
ULT	Urate Lowering Therapy
vWF	Von Willebrand Factor
WHO	World Health Organization

STATISTICAL ANALYSIS PLAN

Protocol No: MEIN/14/FEB-PWV/001 (FORWARD)

Version Number: 2.0

Date of Issue: 2018-03-16

Page 8 of 22

1 STUDY MATERIAL

The following material was considered for this SAP:

Document	Version, Date
Protocol, incl. last amendment	1.4: 2016-03-30
CRF	22-09-2016
DMP	2.0, 2018-01-23
DVP	2.0, 2018-01-23

2 STUDY INFORMATION

2.1 Primary objective

The primary objective is the comparison of the effects of febuxostat and allopurinol on Pulse Wave Velocity (PWV) after 36 weeks of treatment.

2.2 Secondary objective

- Changes in BNP and NTproBNP values after 12, 24 and 36 weeks of treatment
- Changes in inflammation markers (hsCRP, TNF- α , sUA, and plasma fibrinogen) after 12, 24 and 36 weeks of treatment
- Changes in oxidative stress parameters [Malondialdehyde (MDA), Myeloperoxidase (MPO) Oxidized low-density lipoprotein (Ox-LDL), after 12, 24 and 36 weeks of treatment
- Changes in lipid profile after 12, 24 and 36 weeks of treatment
- Percentage of gout patients with a serum urate concentration of less than or equal to 6 mg/dl after 12, 24 and 36 weeks of treatment
- Time to achieve sUA target levels for patients stratified for sUA levels at baseline as follows: 8.1-8.8 mg/dl, 8.9-9.6 mg/dl, 9.7-10.3 mg/dl, 10.4-11.0 mg/dl, >11 mg/dl
- Changes in eGFR with CKD-EPI formula after 12, 24 and 36 weeks of treatment
- Changes in urine albumin excretion as evaluated by first morning urine albumin/creatinine ratio (mg/g) after 12, 24 and 36 weeks of treatment
- Percentage of patients above the sUA target levels at Week 12, Week 24 and Week 36 after having reached the sUA target levels at Week 2
- Tender and swollen joint count

STATISTICAL ANALYSIS PLAN

Protocol No: MEIN/14/FEB-PWV/001 (FORWARD)

Version Number: 2.0

Date of Issue: 2018-03-16

Page 9 of 22

- Pulse Wave Analysis (including modifications of PWV, arterial stiffness, central blood pressure and augmentation index) after 12, 24 and 36 weeks of treatment
- Changes in endothelial activation/adhesion markers (sVCAM, sICAM, vWF, e-selectine) after 12, 24 and 36 weeks of treatment (These parameters will be evaluated in a subset of patients enrolled in selected centers only)
- Safety and tolerability

2.3 Study design

This study is designed as a randomized, active-controlled, open label, evaluator blind, parallel group, multi-center, multi-national, Phase IV trial. Patients will be randomized 1:1 to receive febuxostat or allopurinol.

There will be approx. 35 sites in the following countries: Germany, the Netherlands, Italy, Poland, Serbia, Romania.

Study duration for individual patients will be 39 weeks. This includes a one-week run-in/screening period which can be extended to max 30 days in case of re-testing, followed by a 36 weeks treatment and a 2 weeks safety follow-up (by phone call).

The study physician responsible for randomization and drug supply handling is unblinded to study medications and therefore will not be involved in the main efficacy evaluations of each patient randomized in the study.

Conversely, the study physician/s responsible for the main efficacy evaluation (Pulse Wave Velocity) will be blind to study treatments. In addition, key efficacy variables will be performed by an independent core laboratory where the central reader will be blind to the treatment assigned to patients.

Fasting lipid levels, NTproBNP, BNP, markers of inflammation and endothelial activation/adhesion, oxidative stress parameters, eGFR, changes in urine albumin excretion as evaluated by first morning albumin/creatinine ratio will be also measured by a central laboratory.

Eligible patients will be randomized to treatment with allopurinol 100 mg or febuxostat 80 mg (1:1 ratio). Up-titration of allopurinol or febuxostat to the maximum dose permitted in the study may be performed between Week 2 and Week 10, see flow chart below for details.

A follow-up safety assessment will be performed by a phone call 2 weeks after study termination.

STATISTICAL ANALYSIS PLAN

[figure not shown]
Protocol No: MEIN/14/FEB-PWV/001 (FORWARD)

Version Number: 2.0

Date of Issue: 2018-03-16

Page 10 of 22

Trial flow chart

Notes:

	Day -30 to Week -1	Day 0	Week 2 ± 4 days	Week 12 ± 4 days	Week 24 ± 4 days	Week 36 ± 4 days	Week 38 + 3 days after
	Visit -1	Visit 0	Visit 1	Visit 2	Visit 3	Visit 4	Visit 5 Phone call
	Screening	Randomization	On Treatment Visit	On Treatment Visit	On Treatment Visit	End of Study visit	Safety Follow up
Inclusion/exclusion crit.	X						
Informed consent	X						
Randomization		X					
Medical history	X						
Concomitant medications	X	X	X	X	X	X	
Physical examination	X			X	X	X	
Vital signs (BP, HR body temperature)	X	X		X	X	X	
Height, Body Weight, demography	X						
12-Lead ECG	X						
Pulse Wave Analysis (PWA): PWV, arterial stiffness, central blood pressure, augmentation index		X		X	X	X	
BNP, NTproBNP		X		X	X	X	

STATISTICAL ANALYSIS PLAN

Protocol No: MEIN/14/FEB-PWV/001 (FORWARD)

Version Number: 2.0

Date of Issue: 2018-03-16

Page 11 of 22

	Day -30 to Week -1	Day 0	Week 2 ± 4 days	Week 12 ± 4 days	Week 24 ± 4 days	Week 36 ± 4 days	Week 38 + 3 days after
	Visit -1	Visit 0	Visit 1	Visit 2	Visit 3	Visit 4	Visit 5 Phone call
	Screening	Randomization	On Treat- ment Visit	On Treat- ment Visit	On Treat- ment Visit	End of Study visit	Safety Follow up
Serum Uric Acid	X		X	X	X	X	
Oxidative stress parameters: MDA, MPO, Ox-LDL, PON1 and PON 2		X		X	X	X	
Markers of inflammation: hsCRP, TNF-α, plasma fi- brinogen		X		X	X	X	
Markers of endothelial activa- tion/adhesion: sVCAM, sICAM, vWF, e-selectine (selected sites)		X		X	X	X	
Fasting lipid levels	X			X	X	X	
eGFR		X		X	X	X	
Urine Albumin excretion measured as Albumin to cre- atinine ratio		X		X	X	X	
Tender and swollen joint count		X		X	X	X	
Cigarette smoking, alcohol consumption	X	X	X	X	X	X	X
Urine pregnancy test		X				X	
Safety Laboratory Tests	X			X	X	X	
IMP dispense		X	X	X	X		
IMP accountability			X	X	X	X	
Adverse events	X	X	X	X	X	X	X

NOTES: * screening period lasts up to 7 days but can be extended to max 30 days in case of re-testing of sUA. sUA can be re-tested if current sUA level is changed due to acute (transient) condition as it is not in line previous medical data as per investigator opinion and approval from the Sponsor.

2.4 Planned sample size

A sample size of 79 in each group will have 85% power to detect a difference in means of 1.8 m/sec at Week 36 assuming that the common standard deviation is 3.75 m/sec using a two group t-test with a 0.05 two-sided significance level. Expecting a drop-out rate of approximately 15%, the total number of subjects to be randomized in order to achieve the planned sample size will be 91 per treatment arm, in total 182.

STATISTICAL ANALYSIS PLAN

Protocol No: MEIN/14/FEB-PWV/001 (FORWARD)

Version Number: 2.0

Date of Issue: 2018-03-16

Page 12 of 22

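### Minor arithmetic slip in SAP section 2.4: at 15% drop-out, 91 per arm leaves about 77 patients with observed Week 36 PWV, not 79, and two-group t-test power of about 84%, not 85%

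*SAP*

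**What the plan says.** SAP section 2.4 sizes the trial in two steps.

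- **Evaluable patients.** The requirement reads: "A sample size of 79 in each group will have 85% power to detect a difference in means of 1.8 m/sec at Week 36". Behind it stand an SD of 3.75 m/sec in both arms and a t-test comparing the arms, two-sided at the 5% level.
- **Drop-out.** "Expecting a drop-out rate of approximately 15" per cent, it gives the number to randomise so that this size is reached: "in order to achieve the planned sample size will be 91 per treatment arm, in total 182".

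Section 2.3 fixes equal allocation: "Patients will be randomized 1:1 to receive febuxostat or allopurinol". Section 2.4 does not show how 91 was obtained from 79.

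Three other places bear on who counts as lost. Section 4.2 admits to the full analysis set (FAS) any randomised patient with at least one dose and at least one PWV assessment after randomisation. Sections 5.1.2 and 5.7.1 fill in missing primary-endpoint values by LOCF, and section 5.1.2 also plans an analysis with no imputation. The flow chart in section 2.3 places the first post-randomisation PWV at Week 12.

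**The concern.** The second step claims that 91 randomised patients per arm, less the expected drop-out, give the planned 79. A drop-out rate is a fraction of those randomised, so the number to randomise is the evaluable number divided by one minus the rate. Increasing the evaluable number by the rate itself gives too few. The stated 91 is what that shortcut produces.

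At stake is whether the section's own figures agree. There is no slack to absorb a shortfall, because 79 is the smallest number per arm that reaches 85% power on the stated inputs. Anyone who carries the sentence into a report would state a yield and a power slightly better than the assumptions support.

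**Working it through.** **Inputs**, all from SAP section 2.4 except the allocation (section 2.3): difference δ = 1.8 m/sec; common SD σ = 3.75 m/sec; two-sided α = 0.05; two-group t-test; 1:1 allocation; 79 evaluable per arm; drop-out d of about 15%; 91 randomised per arm, 182 in total.

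**Step 1: reproduce the 79.** With n per arm, the non-centrality is λ = δ / (σ√(2/n)) = 0.48 × √(n/2), on 2n − 2 degrees of freedom. Power is the probability that the non-central t statistic exceeds the two-sided 5% critical value in absolute size.

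- n = 79: λ = 0.48 × √39.5 = 3.017, power 85.04%
- n = 78: λ = 0.48 × √39 = 2.998, power 84.59%
- n = 77: λ = 0.48 × √38.5 = 2.978, power 84.12%

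So 79 is confirmed as the minimum for 85%.

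**Step 2: reproduce the 91.**

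- 79 × (1 + 0.15) = 90.85, rounded up to 91. This matches the SAP.
- 79 / (1 − 0.15) = 92.94, rounded up to 93 per arm, 186 in total. Check: 93 × 0.85 = 79.05, while 92 × 0.85 = 78.2 is still short.

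**Step 3: what 91 per arm leaves.**

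| Drop-out | Remaining per arm, 91 × (1 − d) | t-test power |
|---|---|---|
| 13% | 79.17 | 85.1% |
| 14% | 78.26 | 84.7% |
| 15% | 77.35 | 84.3% |
| 16% | 76.44 | 83.9% |

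Power in the table uses the fractional n. Rounding 77.35 down to 77 gives 84.1%.

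**Step 4: break-even rate.** 91 leaves 79 when d = 1 − 79/91 = 12/91 = 13.2%. Even 14.5%, which still rounds to 15%, leaves 91 × 0.855 = 77.8.

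**Step 5: size of the gap.** 93 − 91 = 2 per arm, or 4 in total. The loss of power is 85.04 − 84.29 = 0.75 points at 77.35 per arm, or 85.04 − 84.12 = 0.92 points at 77.

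**The case against.** The best case for leaving the sentence alone has four parts.

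- **Dropping out is not the same as leaving the primary analysis.** The confirmatory population is the FAS, and LOCF fills in Week 36. A 15% rate means 91 × 0.15 = 13.65 drop-outs per arm. If only two of them have a Week 12 PWV, the LOCF analysis holds at least 79 per arm. This stands, and it limits the point to patients with observed Week 36 data. It does not remove the point: patients who leave before Week 12 have no post-randomisation PWV and fall outside the FAS, the analysis without imputation bears the whole loss, and section 2.4 itself counts the 79 after drop-out. The SAP gives no timing of drop-out, so the FAS number cannot be fixed.
- **The rate is only approximate.** That is true, and 91 is enough up to 13.2%. But no rate that rounds to 15% reaches 79.
- **The primary model is an ANCOVA, not a t-test.** If 3.75 m/sec is an unadjusted SD, which is an assumption, covariates explaining 1 − 77/79 = 2.5% of the variance (a correlation of about 0.16) would make up the loss. This stands as a limit on the claim: the gap is shown for the t-test calculation that section 2.4 states, not for the ANCOVA.
- **The formula is not printed.** Multiplication by 1.15 is inferred from the exact match. The shortfall does not depend on it, because 91 × 0.85 is 77.35 however 91 was obtained.

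**Conclusion.** The point holds as a minor arithmetic error. On the section's own inputs, 91 per arm does not yield 79 after 15% drop-out. It yields about 77 with observed Week 36 PWV, which gives about 84% power for the stated t-test. The matching number to randomise would have been 93 per arm, 186 in total. This rests on reading the drop-out rate as a share of randomised patients and on counting as remaining only those with an observed Week 36 value.

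A reader might go further and infer that the trial is underpowered, or that the primary analysis will hold only 77 per arm. The SAP supports neither. A loss of under one percentage point, at an approximate rate, does not undermine the design. The FAS with LOCF keeps later drop-outs and may reach or exceed 79, and covariate adjustment may recover the lost power.

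**What to change.** Restate the drop-out sentence in SAP section 2.4, without enrolling more patients:

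> With 91 randomised per arm and 15% drop-out, about 77 per arm will have observed Week 36 PWV (about 84% power for the two-group t-test without imputation); 79 per arm (85% power) is reached if drop-out is at most about 13%. The number in the FAS/LOCF analysis may be higher, because patients who drop out after a post-randomisation PWV assessment are retained.

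This costs a short edit to one section and a planned power that reads slightly less favourably. No endpoint, population, model or test changes.

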3 GENERAL INFORMATION

3.1 Background details

The data will be transferred to SAS from the Clinical Data Management System Viedoc. If applicable external data will also be transferred to SAS for presentation of these data in the statistical analyses.

The SAP will be finalized before database lock and unblinding.

3.2 Deviations from the trial protocol with regard to statistical analyses

Due to a misinterpretation by project team the secondary endpoint parameters 'Paraoxonase 1 (PON1)' and 'Paraoxonase 2 (PON2)' were not measured [for enzymatic activity](#), but [genetic tests were performed](#) instead. Since these genetic tests were not planned by the protocol they have not been included in the database nor mentioned in sec 2.2 and 5.7.2. Therefore, no analysis can be performed for PON1 and PON2 as planned in the protocol.

3.3 Individual protocol deviations

Any deviation from protocol will be discussed case by case before database lock or unblinding whether the deviation has to be regarded as minor or as major (and therefore lead to exclusion from particular analysis populations).

The assessment of individual protocol deviations will be made in a Data Review Meeting. A complete listing of protocol deviations and the judgment for assessment of subject disposition will be signed before database lock. All deviations along with the disposition of each subject will be recorded in a separate database member that will become part of the study database. A description of all major protocol violations will be included in the table part of the CSR.

Criteria for major protocol violations will at least include:

- Any substantial violation of in- or exclusion criteria.
- Use of prohibited concomitant medication that may interfere with the assessment of efficacy.
- Receipt of wrong dose of study medication. Randomization errors.
- Trial subjects that developed study withdrawal criteria but were not withdrawn, receipt of wrong dose, use of concomitant medications not allowed
- Non-compliance regarding intake of study drug, i.e. less than 60% or more than 120% of required study drug intake since last visit (see also section 5.3)

STATISTICAL ANALYSIS PLAN Protocol No: MEIN/14/FEB-PWV/001 (FORWARD)	
Version Number: 2.0 Date of Issue: 2018-03-16	Page 13 of 22

Version Number: 2.0	Page 13 of 22
Date of Issue: 2018-03-16	

Any deviation from the protocol (to be classified as major or minor) will be accepted only in case of emergency and/or after a written agreement with the Sponsor.

4 ANALYSIS POPULATIONS

The disposition of subjects will be displayed according to the following analysis populations:

- Safety (SAF) population,
- Full Analysis Set (FAS),
- Per-Protocol (PP) population.

4.1 Safety population

All patients randomized to any of the two treatment groups and having taken at least one dose of IMP.

4.2 Full analysis set population

The full analysis population (FAS) includes all randomized patients who have taken at least one dose of IMP. and performed at least one primary efficacy assessment (PWV) after randomization.

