4.3 Per-protocol population

The per-protocol (PP) populations are a subset of the FAS population.

Two separate per-protocol populations will be considered:

Per-protocol population 1 (PP1) includes all patients randomized to either of the two treatment groups and having completed the study without any major protocol violation as per blinded data review meeting. Patients must have completed all the planned study visits and have been evaluated for the primary endpoint of the study at the final visit.

Per-protocol population 2 (PP2) includes all patients randomized to either of the two treatment groups and having completed the study without major protocol violations which might have an impact on the evaluation of the primary objective of the study.

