5.7 Efficacy

The efficacy evaluation of the primary endpoint will be performed in both FAS and PP Populations. The Full Analysis Set (FAS) will be the primary analysis population for the confirmatory analysis. A sensitivity analysis based on the Per-Protocol 2 (PP2) population will be performed.

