5.7.2 Secondary endpoints

All secondary efficacy variables will be analyzed based on the FAS population.

For the analysis of continuous secondary efficacy variables, the ANCOVA model with change from baseline to respective time point as a response variable and respective baseline value and treatment group as the terms in the model will be used at each time point for the parameters listed below. The LOCF method will be used for missing data imputations.

- Changes in BNP and NTproBNP values after 12, 24 and 36 weeks of treatment
- Changes in inflammation markers (hsCRP, TNF- α , sUA, and plasma fibrinogen) after 12, 24 and 36 weeks of treatment
- Changes in oxidative stress parameters [Malondialdehyde (MDA), Myeloperoxidase (MPO) Oxidized low-density lipoprotein (Ox-LDL),] after 12, 24 and 36 weeks of treatment
- Changes in lipid profile after 12, 24 and 36 weeks of treatment
- Changes in eGFR with CKD-EPI formula after 12, 24 and 36 weeks of treatment
- Changes in urine albumin excretion as evaluated by first morning urine albumin/creatinine ratio (mg/g) after 12, 24 and 36 weeks of treatment
- Pulse Wave Analysis (including modifications of PWV, arterial stiffness, central blood pressure and augmentation index) after 12, 24 and 36 weeks of treatment
- The primary parameter PWV over time (12 to 36 weeks) will be analyzed using a repeated measurement model
- Changes in endothelial activation/adhesion markers (sVCAM, sICAM, vWF, e-selectine) after 12, 24 and 36 weeks of treatment (These parameters will be evaluated in a subset of patients enrolled in selected centers only)
- Tender and swollen joint count

Logistic regression will be used to analyze the parameters below for the difference between treatment groups at each time point where the dependent variable is defined as a binary outcome (e.g. 1 if urate concentration ≤ 6 mg/dl, 0 otherwise) and treatment group and baseline urate concentration will be included as independent variables.

- Percentage of gout patients with a serum urate concentration of less than or equal to 6 mg/dl after 12, 24 and 36 weeks of treatment
- Percentage of patients above the sUA target levels at Week 12, Week 24 and Week 36 after having reached the sUA target levels at Week 2

STATISTICAL ANALYSIS PLAN

Protocol No: MEIN/14/FEB-PWV/001 (FORWARD)

Version Number: 2.0

Date of Issue: 2018-03-16

Page 19 of 22

Proportional hazards model with treatment group as covariate will be used to investigate:

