- Time to achieve sUA target levels for all patients with baseline sUA as additional covariate
- Time to achieve sUA target levels stratified for sUA levels at baseline as follows: 8.1-8.8 mg/dl, 8.9-9.6 mg/dl, 9.7-10.3 mg/dl, 10.4-11.0 mg/dl, >11 mg/dl
- Time to achieve sUA target levels for all patients and stratified for sUA levels at baseline as follows: >8 and <9 mg/dl, >9 and <10 mg/dl, ≥ 10 mg/dl will additionally be presented

In case of deviation from proportional Hazard-assumption the log-rank-test will be used instead.

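### The FAS requires a post-randomisation PWV, first scheduled at Week 12, so patients who leave after the Week 2 sUA but before any such PWV drop out of every sUA analysis

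*SAP*

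**What the plan says.** SAP section 4.2 states that the FAS "includes all randomized patients who have taken at least one dose of IMP", and adds a second condition: the patient must have "performed at least one primary efficacy assessment (PWV) after randomization".

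The flow chart in section 2.3 fixes when each condition can be met. The row "Pulse Wave Analysis (PWA): PWV, arterial stiffness, central blood pressure, augmentation index" is marked at Day 0 and then at Weeks 12, 24 and 36. The row "Serum Uric Acid" is marked at screening and at Weeks 2, 12, 24 and 36.

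Section 5.7 says of the primary endpoint: "The Full Analysis Set (FAS) will be the primary analysis population for the confirmatory analysis". Section 5.7.2 extends the same set to everything else: "All secondary efficacy variables will be analyzed based on the FAS population". No exception is made for sUA. The per-protocol sets bring nobody back, because section 4.3 states: "The per-protocol (PP) populations are a subset of the FAS population".

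The sUA endpoints in section 5.7.2 are:
- change in sUA at Weeks 12, 24 and 36;
- the proportion at or below 6 mg/dl at those visits;
- loss of target among patients at target at Week 2;
- time to target, whose first listed analysis is "Time to achieve sUA target levels for all patients with baseline sUA as additional covariate".

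Sections 5.1.2 and 5.7.2 prescribe LOCF for missing secondary data.

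**The concern.** An analysis set that requires a post-baseline value of the endpoint being analysed is common practice. Here the condition belongs to a different endpoint. None of the sUA analyses needs a PWV, yet a patient without one is removed from all of them.

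The timing makes this matter. The condition can first be met ten weeks after the first on-treatment sUA. For time to target, membership of the analysis set is decided by something that happens after the event may already have occurred. Section 2.3 also places up-titration between Week 2 and Week 10, so the FAS selects patients who stayed in the study through titration. Patients and treating physicians know the treatment, and early departure could differ between arms for reasons linked to tolerability or response. Blinded reading of PWV does not protect against that. If departure does differ, the sUA comparisons are no longer between the groups as randomised.

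**Working it through.** **Step 1: what happens to one patient.** Take a dosed patient who attends Week 2, has sUA measured, and leaves the study before any post-randomisation PWV.

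| Endpoint | What the patient could contribute | What the plan does |
|---|---|---|
| Time to sUA target | An event at Week 2 if at target, otherwise censoring at Week 2 | Excluded; observed data lost |
| sUA response and change at Weeks 12, 24, 36 | No value at these visits; only a Week 2 value carried forward, or a count as not at target | Excluded; absent from the denominator |
| Loss of target after Week 2 | Only the qualifying Week 2 status | Excluded |

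The loss of observed data is outright only in the first row. In the others the issue is who is in the denominator and how missing values are treated.

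**Step 2: the plan's sample size.** Inputs from section 2.4: difference 1.8 m/sec, SD 3.75 m/sec, two-sided alpha 0.05, power 85%.
- Normal approximation: n = 2 × (1.960 + 1.036)² × 3.75² / 1.8² = 77.9, so 78 per group.
- Exact two-sample t-test: n = 79 gives power 0.850 and n = 78 gives 0.846, so 79 per group. The stated figure is reproduced.
- Inflation: 79 × 1.15 = 90.9, so 91 per arm and 182 in total, as stated.

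**Step 3: how many patients may be affected.** Drop-outs implied by the plan: 0.15 × 182 = 27.3, about 27. The SAP does not say when they occur, so timing is an assumption.

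Uniform drop-out over 36 weeks:
- before Week 12: 27.3 × 12/36 = 9.1, which is 5.0% of 182;
- before Week 2: 27.3 × 2/36 = 1.5;
- between Weeks 2 and 12: 27.3 × 10/36 = 7.6.

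The last group, about 7 to 8 patients, would normally have an sUA result that the FAS definition discards.

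Other timings:

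| Share of drop-outs before Week 12 | Patients | % of 182 |
|---|---|---|
| 0% | 0 | 0.0 |
| 25% | 6.8 | 3.8 |
| 33% | 9.1 | 5.0 |
| 50% | 13.7 | 7.5 |
| 100% | 27.3 | 15.0 |

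The visit windows are ±4 days, so Week 2 and Week 12 here mean those visits, not exact days.

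**The case against.** Several counter-arguments have weight.

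**The condition is about PWV, not about drug.** A reader might infer that everyone who stops treatment in the first 12 weeks is excluded. Section 4.2 does not say so. A patient who stops the drug but attends Week 12 for PWV stays in the FAS, as does one who misses Week 12 and has a PWV later. This stands: the point concerns leaving the study.

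**The protocol may take a PWV at early withdrawal.** The SAP's flow chart shows no such visit, but it lists scheduled visits only and the protocol is not at hand. If there is one, some early leavers enter the FAS and the count falls. This limits the size of the problem. It does not remove the dependence of the sUA analyses on PWV.

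**For response and change, little observed information is lost.** A patient gone before Week 12 has no sUA at Weeks 12 to 36. Under the plan's LOCF rule, including the patient would carry forward a Week 2 value that precedes titration, which is no clear gain. This also stands, and is why the remedy for response has to address the missing-data rule as well as the population.

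**The confirmatory analysis is untouched.** The endpoints concerned are secondary. For PWV itself, requiring a post-randomisation value is defensible. This stands too.

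A reader might also want to state a percentage-point bias in the responder comparison. The SAP gives neither response rates nor early loss by arm. A calculation that counted leavers as non-responders would mix the effect of the FAS definition with a rule that the plan does not use.

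**Conclusion.** The point holds for the sUA endpoints. Read as written, the SAP excludes from all of them any dosed patient who leaves after the Week 2 sUA and before a post-randomisation PWV. The consequence is clearest for time to target: an analysis described as covering all patients omits real Week 2 events and censoring times. For response and change, early leavers are missing from the denominators of an open-label comparison.

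The size is modest: about 9 of 182 patients before Week 12, about 7 to 8 of them after Week 2, if the 15% drop-out is uniform over 36 weeks. The range before Week 12 is 0 to 27 for other timings, and lower if PWV is taken at early withdrawal. Neither the direction nor the amount of any bias can be derived from the SAP; bias arises if early departure differs between arms. The documents do not support extending the point to the primary PWV analysis or to patients who merely stop treatment.

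**What to change.** Keep the FAS for PWV. In sections 4.2 and 5.7.2, state that the sUA endpoints, above all time to target, are analysed in all randomised patients with at least one dose, by randomised arm, without the PWV condition. Section 4.1 already defines a set with this membership for safety; what must be added is its use for sUA and the grouping by randomised arm.

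Then specify:
- **Time to target:** censor patients who have not reached target at their last sUA.
- **sUA response at Weeks 12, 24 and 36:** count patients with no sUA at the visit as not at target, at least as a sensitivity analysis beside LOCF, because a carried-forward Week 2 value precedes titration. Adjust section 5.1.2 to match.
- **Early withdrawal:** if the protocol takes a PWV at that point, say in section 4.2 that it counts towards the FAS.

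The change needs SAP wording and uses data already planned for collection. There are two costs. The sUA and PWV tables will have different denominators, although section 8.2 already requires both the population size and the number contributing on each output. In addition, section 3.2 declares only the PON1 and PON2 change, which suggests that the FAS definition comes from the protocol. If so, the new population must be listed there as a further deviation, before database lock.
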